2.3.2 Potential Benefits

Initial studies suggest efficacy of topical application of timolol in the treatment of IH, improving both the color and the volumetric size of the lesion. Treatment may also prevent functional complications. Topical treatment of IH with beta blockers will likely have an improved safety profile when compared to oral therapy although transcutaneous absorption has not been fully characterized. Conclusions drawn from this study will benefit infants receiving timolol in the future through better understanding of the efficacy and the characterization of the safety and PK profile of two different formulation strengths of this drug.

3 OBJECTIVES

Primary: Describe the efficacy of 0.25% and 0.5% topical timolol maleate GFS as assessed through IH changes in volume.

Secondary: Describe the safety of topical timolol maleate GFS for treatment of IH.

Exploratory: Describe the PK of topical timolol maleate GFS for treatment of IH.

3.1 Study Outcome Measures

3.1.1 Primary Efficacy Outcome

Partial response of hemangioma volume from baseline to 180 days within each treatment arm and compared with untreated controls.

3.1.2 Secondary Outcome Measures

1. Efficacy

- Partial response of hemangioma color from baseline to 180 days within each treatment arm and compared with untreated controls
- Comparison of partial response of hemangioma volume from baseline to 180 days between the two treatment arms
- Comparison of partial response of hemangioma color from baseline to 180 days between the two treatment arms
- Improvement of hemangioma complication in infants within each treatment arm
- Assess time to partial response by comparing baseline to day 30, day 60, day 120 and day 180 in both treatment arms
- Hemangioma Quality of Life assessment for infants within each treatment arm

- ###### 2. Serious adverse events and adverse events of special interest in infants treated with topical timolol maleate (0.25% and 0.5%) GFS for the treatment of infantile hemangioma

3.1.3 Exploratory Outcome Measures

- Pharmacokinetics: Clearance (CL), Volume of distribution (V), Area under the curve (AUC), Maximum concentration (C_{max})
- Relationship between hemangioma characteristics and plasma concentrations

4 STUDY DESIGN

4.1 Study Design

This is a prospective, multi-center, double-masked, randomized, efficacy, safety, and PK study. Infants who satisfy all eligibility criteria will be randomized (1:1) to 0.25% or 0.5% timolol GFS and will be treated for a period of 180 days (Figure 1).

Randomization will be stratified using two age groups: <4 weeks postnatal age and ≥4 weeks postnatal age. Infantile hemangiomas are more common in preterm and low birth weight infants, therefore, it is expected that 10% of enrolled subjects will be preterm infants. Infants who are eligible for the study based on inclusion and exclusion criteria but whose parents decline treatment of the hemangioma will constitute the non-intervention arm of the study and will serve as a control group.

Infants who have progressive disease and require additional therapy as determined by the treating physician will be unmasked: if on the 0.25% timolol maleate GFS they will receive open label 0.5% timolol GFS two times a day and continue to be followed per the schedule of study procedures (Table 6-1). If they are on 0.5% the investigator may choose to continue the 0.5% open label or withdraw the participants from the Treatment Phase and proceed into the safety follow-up period and receive alternate therapies.

This study will be conducted in accordance with current U.S. Food and Drug Administration regulations and guidelines, (or, as applicable, international regulations and associated guidelines), the International Council for Harmonisation Guidelines on Good Clinical Practice (which incorporate the principles of the Declaration of Helsinki), as well as all other applicable national and local laws and regulations.

4.1.1 Study design for Control Cohort

Previous experience with clinical trials designed for IH treatment and performed in the US have demonstrated that parents are unlikely to enroll in double-masked, randomized, placebo- controlled studies. Therefore, two different strategies will be implemented to obtain age- matched control data. One strategy will include sharing of data and clinical photographs from two other completed randomized, placebo controlled studies in infants with IH. The patients in these studies are of similar age to our study and present similar IH characteristics. For the purpose of this study, the control group and the placebo groups from the two similar studies will serve as the untreated control cohort in our study.

[figure not shown]
The first study identified is a recently completed prospective, single-center, double-masked, randomized, placebo-controlled efficacy study in Barcelona, Spain (Efficacy and safety of topical administration of timolol maleate 0.5% solution in the treatment of Child Proliferative Hemangioma Early Stage Surface. Randomized Controlled Study). This study has enrolled a total of 70 patients, 35 randomized to 0.5% timolol BID and 35 to placebo BID for 6 months. (EudraCT Number: 2013-005199-17). In addition, photographs from a second previously published double-masked, randomized, placebo-controlled trial (Australian and New Zealand Clinical Trials Registry Number: ACTRN12610001069044) are anticipated to be provided for analysis.²⁰ These studies are anticipated to provide paired clinical photographs of approximately 35 placebo-treated patients through up to 180 days following baseline.

As a secondary strategy, approximately 10 infants who are eligible for this study based on inclusion and exclusion criteria, but whose parents decide not to treat the IH, will be enrolled and also serve as a part of the untreated control cohort.

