Efficacy of topical application of timolol for IH: Numerous case reports and small studies, including those of premature infants, have reported growth arrest and reduction in thickness and redness of IH within 2 weeks to 4 months topical application timolol maleate, particularly in superficial lesions.¹³⁻¹⁸ As a result, existing prospective studies of topical timolol for IH have focused on application to superficial IH rather than deeper lesions. In the largest available prospective study of 124 Chinese infants with IH, administration of timolol therapy directly to the IH for 4 months resulted in controlled growth of IH in 36/101 (36%) infants, and regression of IH in 56/101 (56%) infants. Only 3/23 (13%) infants in the control group had regression of IH.¹⁸ In a retrospective study, investigators treated 73 infants (median age 4.3 months, 25th, 75th percentiles: 2.6, 7.2 months) for a mean of 3.4 months, and the mean visual analogue scale improvement at the last follow-up visit was 45%.¹⁹ Previous investigators also conducted a prospective, placebo-controlled analysis of topical timolol efficacy in 41 infants, ages 5 to 24 weeks. Among those who received treatment, a higher proportion of IH decreased in size as assessed by the visual analog scale by >5% at week 20 compared to those who did not receive treatment, $p < 0.02$.²⁰ In a study of 25 infants treated for 6 months, timolol was more effective when applied to thinner, plaque-type morphology than nodular superficial lesions.¹⁷

Outcome scales used to assess efficacy of treatment for IH:

Because most of the growth observed in IH is in tumor thickness not width, assessment of IH progression or regression has proven difficult with standard methods of measurement. Therefore, investigators have developed several scales to assess IH growth and efficacy of treatment for IH. All available scales are based on a shared concept of visual changes (progression or regression) at the determined endpoint compared to baseline or time zero, and aim to convert subjective improvement or worsening to quantitative measures. The

[figure not shown]

Figure 1. IH on tip of nose, cheek and eyelid demonstrating 3 dimensional growth over 3 week period.

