The visual analog scale (VAS) methodology is a widely accepted and frequently used measurement instrument for assessment of IH growth. When responding to a VAS item, raters specify the level of change from time zero to the endpoint (growth or regression) by indicating a position along a continuous line between two end-points. The best results are observed when lesional photographs are taken and a centralized assessment is made by unbiased, masked, and well-trained investigators. Although not formally validated, the VAS methodology has been used in several IH studies to evaluate response of IH to treatment with both topical and oral therapies. Most recently, a centralized VAS methodology was used in a study to gain FDA approval for an oral propranolol formulation for treatment of IH. Further, the VAS has demonstrated good agreement between masked observers, based on the intraclass correlation coefficient.^{19,21,22} Studies have demonstrated the best interreader and intrareader reliability when primary efficacy is assessed by trained and validated raters using standardized digital photographs.²³

Safety of topical application of timolol for IH: In contrast to oral propranolol for which safety data from a completed industry-sponsored trial exists, publications reporting the efficacy of topical timolol have not been subjected to the usual stringency of Phase 1/2/3 clinical trials. In addition, these studies have been relatively small in size and short in duration, with no pharmacokinetic data and little to no prospective safety monitoring; therefore, rare adverse events (AEs) may have been missed.

In a prospective study of 124 infants, parents reported no AEs related to study drug administration,

although investigators did not formally monitor bradycardia or hypotension.¹⁸ In the retrospective analysis of 73 infants, parents reported sleep disturbance in one subject, but investigators reported no other AEs in the cohort.¹⁹ In the prospective trial of 41 young infants, only 19 of whom were treated, investigators monitored heart rate and blood pressure at specified intervals until the end of the study.²⁰ There were no significant differences in heart rate or blood pressure between the treatment and observation groups.²⁰

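### The external controls are called age-matched, but no age limit applies to them and one source enrolled at 5 to 24 weeks against 0-84 days here, so the unadjusted primary tests may include over-age controls

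*Combined protocol and SAP*

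**What the plan says.** Section 4.1.1 explains that a placebo arm was thought hard to recruit, so "two different strategies will be implemented to obtain age- matched control data". The main strategy is "sharing of data and clinical photographs from two other completed randomized, placebo controlled studies", whose patients are described thus: "The patients in these studies are of similar age to our study and present similar IH characteristics". One source is the Barcelona trial, with 35 placebo infants and no ages given. The other is described as "photographs from a second previously published double-masked, randomized, placebo-controlled trial". Together they are "anticipated to provide paired clinical photographs of approximately 35 placebo-treated patients through up to 180 days following baseline". About 10 eligible infants whose parents decline treatment complete the cohort.

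Section 2.1 describes the second source, which carries the same reference number in both places, as a "placebo-controlled analysis of topical timolol efficacy in 41 infants, ages 5 to 24 weeks".

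This trial enrols at 0-84 days (5.2.1). That criterion is tied to the first study dose or to entry into the non-intervention cohort, and neither event applies to an external control. Section 10.4.1 adds no age rule. Randomisation is stratified at 4 weeks (4.1, 5.3.2).

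Sections 10.2 and 10.4.4 test the response proportions by chi-square or Fisher's exact test. Section 10.4.4 also commits to logistic regression including postnatal age, as a further analysis, and to assessing differences between the control studies. Section 6.6 has all images, controls included, rated centrally by masked raters.

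**The concern.** Randomisation protects only the comparison of 0.25% with 0.5%, which is secondary. Both primary comparisons depend on the control cohort being like the treated infants, and about 35 of 45 planned controls (78%) come from elsewhere. The plan rests that likeness on an age match for which it gives no rule, and its own background section conflicts with the match for one source.

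Age could matter here. Section 2.1 places active growth at 0-3 months. An infant who enters at, say, 20 weeks is past that window and might regress more over the next six months than one who enters at 4 weeks. The control response rate would then be too high for this trial's population, the timolol effect would be understated, and the primary p-values would carry that error. The regression would show it only as a secondary result.

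**Working it through.** **1. The plan's own power.** Inputs from 10.3: 35 evaluable controls at 0.15; 45 per arm at 0.45 (0.25%) and 0.50 (0.5%). Alpha is 0.05/2 = 0.025 per hypothesis (10.2). Exact binomial enumeration of the Pearson chi-square test, one-sided at 0.025, gives 92.9% (0.5% arm) and 84.3% (0.25% arm), against the stated 93% and 85%. The figures reproduce, with no allowance for non-randomised controls. With 45 controls the same calculation gives 96.1% and 89.8%.

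**2. Age overlap.** 5 to 24 weeks is days 35-168, a span of 133 days. The overlap with 0-84 is days 35-84, or 49 days: 49/133 = 37% of the source's range and 49/84 = 58% of this trial's. The second source can supply no infant under 4 weeks.

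**3. How many over-age controls.** Section 2.1 says of the second source: "In the prospective trial of 41 young infants, only 19 of whom were treated". It can therefore supply at most 41 - 19 = 22 placebo infants; the actual number may be anything from 0 to 22. Two assumptions are needed:
- ages uniform over days 35-168, so the over-age share is (168 - 84)/133 = 0.632;
- either 35 of the 35 + 22 = 57 placebo infants are taken in proportion, giving 22/57 x 35 = 13.5 from this source and 13.5 x 0.632 = 8.5 over age; or all 22 are used, giving 22 x 0.632 = 13.9.

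**4. Effect on power.** Assume over-age controls respond at r instead of 0.15. The control rate becomes 0.15 + (8.5/n)(r - 0.15), where n is the number of controls.

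| Controls | r | Control rate | Benefit understated by | Power 0.5% / 0.25% |
|---|---|---|---|---|
| 45 | 25% | 0.169 | 1.9 points | 93% / 85% |
| 45 | 35% | 0.188 | 3.8 points | 90% / 79% |
| 45 | 45% | 0.207 | 5.7 points | 85% / 71% |
| 35 | 25% | 0.174 | 2.4 points | 88% / 76% |
| 35 | 35% | 0.199 | 4.9 points | 81% / 67% |
| 35 | 45% | 0.223 | 7.3 points | 73% / 57% |

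The rate of false claims of benefit, with treated infants at 0.15, stays below 0.025 in every row (at most 0.015).

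**5. Does an age limit alone repair it?** A simulation took treated infants and other controls as uniform over 0-84 days, the second source as uniform over 35-168 days under the plan and 35-84 under the limit, and log-odds of response linear in age. The true difference for the 0.5% arm is 0.35. For odds ratios of 1, 1.5 and 2 per 42 days:
- as planned (21 + 14 = 35 controls), the unadjusted difference averages 0.35, 0.31 and 0.28;
- with the age limit and the same chi-square test (22 + 5 = 27 controls), it averages 0.35, 0.35 and 0.34, with power of 86-88%.

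A penalised (Firth) logistic model with age in the limited cohort gave standardised differences of 0.336, 0.333 and 0.337 with similar power. The age limit does nearly all the work.

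**The case against.** The best defence is that nothing may be wrong in practice. Barcelona alone has 35 placebo infants, exactly the number assumed in 10.3, so the second source may contribute none. An enrolment range is not an age distribution. The over-age response rates are invented. This stands: the size cannot be established from the documents.

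The case for an age effect is also thin. The involution remark in 2.1 concerns thicker lesions, while this trial takes only lesions under 2 mm. The same paragraph names initial thickness as the only significant predictor of early improvement in size. That stands too, although those infants were treated and the covariates tested are not listed.

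Third, an age-adjusted estimate and a between-study check are already planned, and rating is masked. This lessens the concern but leaves the primary tests unadjusted, and the between-study check has no stated method or consequence.

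A reader might infer more than the documents support:
- *That the primary tests are biased towards timolol.* By the age route described, the bias runs against it. Differences between studies, or parental choice, could act either way, but that is a separate matter which age does not settle.
- *That the regression must become the primary analysis.* Step 5 does not support this; once the age limit applies, adjustment changes little.
- *That the second trial ended at week 20.* Section 2.1 says only that more treated lesions had "decreased in size as assessed by the visual analog scale by >5% at week 20". It gives a time of assessment, not the end of follow-up.

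**Conclusion.** The concern holds as a gap in specification that should be fixed. The age-matched description has no rule behind it and conflicts with the plan's own account of one source. As written, infants older than 84 days can enter both primary comparisons without adjustment. The randomised comparison of the two strengths is unaffected.

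With 8.5 over-age controls, power falls from 96%/90% to between 93%/85% and 85%/71% if 45 controls are evaluable, and from 93%/84% to between 88%/76% and 73%/57% if 35 are. In the mildest case with 45 controls nothing is lost against the stated 93%/85%. All of this rests on an assumed split between sources, uniform ages and an assumed age effect. If any of these fails, the loss may be smaller, larger or nil.

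**What to change.** 1. In 4.1.1 and 10.4.1, admit external placebo infants to the primary control cohort only if their baseline age is 0-84 days. Confirm that baseline age can be obtained for the second source, for which 4.1.1 names only photographs. Correct the wording on similar age and age matching, and state each source's age range.
2. In 10.2 and 10.4.4, keep chi-square or Fisher's test as primary in the age-limited cohort, and name the planned age-adjusted logistic regression as a key sensitivity analysis reported beside it. A penalised fit is optional: at 15%, 21 to 36 controls give only about 3 to 5 responders.
3. Apply the 10.1 failure rules to external controls who left their trial early as they are applied to treated infants. Dropping such controls would introduce a new bias: if 10-20% left as non-responders (an assumption), the retained control rate would rise from 15% to 0.15/0.90 = 16.7% or 0.15/0.80 = 18.8%. Do not count as a drop-out a control who completed a trial with shorter planned follow-up, and report how many there are.
4. State that neither the age limit nor the regression removes confounding by study or by parental choice.

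The cost is protocol and SAP wording, one data request and fewer controls, so power must be restated. At a 15% control rate and 45 per arm (0.5%/0.25%):
- 36 controls (45 less 8.5): 93.6%/85.5%
- 31 (45 less 13.9): 91%/81%
- 27 (35 less 8.5): 88%/77%
- 21 (35 less 13.9): 82%/70%

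The stated figures are 93%/85%. Any Barcelona infants over 84 days would lower these further and cannot be counted from the documents.

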4.2 Duration of Study Participation

Duration of infant participation in the study is up to 270 days for infants in the treatment arms (180 days of study drug, 7 days of safety monitoring after last study dose for all adverse events and 90 days of safety monitoring after last study dose for adverse events of special interest) or 180 days for infants in the non-intervention arm.

Figure 1.

¹Infants that cross from randomized, masked timolol maleate GFS to open label 0.5% timolol maleate GFS will continue to be followed per the schedule of study procedures (Table 6-1).

5 STUDY POPULATION

5.1 Selection of the Study Population

Young infants with superficial small hemangiomas in the proliferative phase and who have been identified by their treating physician as needing topical treatment with timolol maleate GFS will be considered for the study. For infants with more than one lesion, a target lesion (a lesion that will require treatment with study drug) will be identified. The infants will be administered study drug only on that lesion. Infants who are eligible for the study based on inclusion and exclusion criteria but whose parents decline treatment with timolol will be included in the non-intervention (control group) in the study.

The majority of recruitment is anticipated to be from outpatient pediatric dermatology clinics, but additional recruitment may occur from inpatient units including the newborn nursery and neonatal intensive care units.

5.2 Inclusion/Exclusion Criteria

5.2.1 Inclusion Criteria

1. Documented informed consent from legal guardian
2. 0-84 days postnatal age at time of first study dose or when enrolled into the non-intervention cohort.
3. Clinical diagnosis of superficial cutaneous or mucosal infantile hemangioma: (must include all of the following):
 - a. superficial lesion in the dermis of the skin
 - b. thin (<2 mm in thickness)
 - c. $\geq 0.5\text{cm}$ at its longest dimension and $\leq 10\text{ cm}^2$
 - d. Involves skin or keratinized mucosa

5.2.2 Exclusion Criteria

1. History of previous treatment with any pharmacologic or laser therapy for IH
2. Ongoing therapy with an oral beta blocker or oral corticosteroid (e.g., cardiac arrhythmia, adrenal insufficiency, upper airway obstruction, tetralogy of fallot, hypertension, reactive airways disease)
3. IH that requires systemic therapy (defined by dynamic complication scale >3)
4. Infants with more than one hemangioma that requires therapy
5. IH of the non-keratinized mucosa
6. Hemodynamically significant cardiovascular disease, as determined by the investigator
7. Known allergy to beta blockers or vehicle
8. Heart rate <100 beats per minute at screening visit
9. Known prenatal or postnatal diagnosis of 2nd/3rd degree atrioventricular block
10. History of reactive airway disease (RAD)
11. Any condition which would make the participant, in the opinion of the investigator, unsuitable for the study

5.3 Treatment Assignment Procedures

5.3.1 Additional Participants

If more than 10 total treated infants are withdrawn on or before the Day 30 visit or 20 total treated

infants are withdrawn at any time in the study for reasons other than lack of efficacy after randomization, additional infants may be enrolled. All infants receiving ≥ 1 dose of study drug will have safety follow up for at least 7 days after the last dose.

5.3.2 Randomization Procedures

Patients meeting eligibility criteria whose parents agree to treatment with timolol will be randomized in a 1:1 ratio to 0.25% or 0.50% timolol GFS. Randomization will be stratified by study site and age group: <4 weeks postnatal age vs ≥ 4 weeks postnatal age at time of randomization.

The infant's randomized treatment assignment will be obtained through the Advantage eClinicalSM enrollment module. In the event that Advantage eClinicalSM is not available at the time of randomization, a back-up system specified in the MOP will be used.

5.3.3 Reasons for Participant Withdrawal

5.3.4 Withdrawal from Treatment Phase (study drug dosing)

The clinician or family may choose to suspend study drug dosing for any reason during the study period, and the infant will remain in the study.

If at any time during the study, the treating physician determines that the target hemangioma failed therapy and the IH requires more aggressive surgical or alternate pharmacologic therapy (e.g., oral beta blockers, or oral or topical corticosteroids), the infant may be withdrawn from the Treatment Phase and move into the 7 day safety follow-up period. If the participant continues to participate in the study, they will be followed for safety for 7 days after last study dose, and should continue to return for planned study visit activities including photography of the IH.

If a treating physician chooses to withdraw the participant from the Treatment Phase (i.e. discontinue timolol maleate GFS dosing), the treating physician must immediately report this to the DCRI study PI and Protocol Chairs.

The investigator will withdraw a participant from receiving further study drug if:

1. Any clinically significant adverse event (AE) is deemed by the principal investigator to require discontinuation of study drug.
2. The treating physician determines that the target hemangioma failed therapy and requires alternate pharmacologic, laser or surgical intervention.
3. Participant develops ulceration of the target hemangioma after therapy is initiated.
4. Participant receives oral or intravenous corticosteroids or additional oral, intraocular, or topical beta blockers for treatment of any other conditions.
5. Requested by the NIH, FDA, DMC, or PTN.

